Participants and study staff assessing outcomes will be blinded to intervention status. Research assistants on the study staff will add the sleep education handouts with video links to discharge instructions to be delivered by the bedside nurse in concurrence with clinical care. The intervention was designed this way to increase feasibility and generalizability for the future by providing a means of information dissemination that could be easily and widely adopted if effective within different health systems in conjunction with clinical care. This research assistant will be notified by REDCap when a participant is enrolled, and will place instructions in the discharge section of the electronic health record that is automatically printed at discharge, without interaction with other study team members or families. Additionally, this portion of the intervention will be delivered at hospital discharge concurrent with clinical care to improve generalizability in future work by limiting change to institutional care practices. The sleep handout will be delivered in conjunction with standard discharge instructions provided to all TBI patients and other care will remain per our institutional TBI standards directed by the

patient's care team (an example of these standard TBI discharge instructions are uploaded in supporting documentation).

Outcomes: We will include measures of feasibility, acceptability, and effectiveness. See **Table 1** for summary of outcomes and schedule of collection. Outcomes will be assessed at hospital discharge, and a study visit at 30 days \pm 17 days. 30-day outcomes assessments will be defined from the time of study intervention initiation. The primary outcomes will be measures of feasibility and acceptability, with exploration of effectiveness in this pilot trial. Quantitative measures of recruitment and retention (feasibility), adverse events and utilization (acceptability), and total score of the Sleep Disturbances Scale for Children (SDSC) at 30-days (clinical effectiveness) will be used. Outcomes will be collected by the study team over the phone, via chart review, or via electronic survey administered through REDCap. Secondary and other outcome measures will be collected by activity monitor, chart review, survey, sleep questionnaire, and actigraphy devices. Fitbits will be worn continuously during the 30 day study period except when removed for charging the device.

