Text messaging will be used for system generated reminder prompts such as "Please sync your device"; or if battery is low, "Please charge your battery" during the 1-month study period while participants wear the Fitbit. Text messaging functions require sharing of participant phone numbers with the Fitabase platform and Twilio, Inc.

Feasibility benchmarks will be assessed every 6 months during the trial. If feasibility benchmarks are not met, study procedures and the protocol will be reviewed using input from stakeholders and preliminary data to determine if changes are warranted.

Table 1. Outcomes Evaluation and Analysis for Melatonin Trial

Outcome (time collected)	Measurement or Assessment Tool	Analysis
Feasibility Outcomes		
*Recruitment (6-monthly feasibility reviews)	Number subjects consented/approached; goal >50%	Descriptive percent
*Retention (6-monthly feasibility reviews)	Quantitative Number completed/consented; Goal >90%	Descriptive percent
Screen failure (6-monthly feasibility reviews)	Number approached/eligible patients; expect <<5%; eligible patients will be derived from the OHSU Trauma Registry and compared to study logs	Descriptive percent
Reasons for Participation/ Non-participation (time of approach/consent)	Qualitative response to survey: "Please describe reasons you chose [not to or to] participate in this research study"; "Could the study team do something different in the future to increase chances you would participate in future studies?"	Thematic analysis
Reasons for drop-out (30-day)	Qualitative response to survey: "We would like to know how we can improve our study in the future. Please tell us your reasons for leaving the trial"; "How could the study team have assisted you better in completing the trial?"	Thematic analysis
Adherence (30-day)	Pill counts: adherent if \geq 75% prescribed pills are taken at the follow-up study visit; will be counted as unknown if pill count not available Sleep tracking usage: actigraphy data and sleep diaries will be compared to age based recommendations; actigraphy counted as	Descriptive percent; Chi-square to compare intervention arms Descriptive percent; Chi-square to compare intervention arms

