Subjects can withdraw from the study at any time, including discontinuation of the intervention. Subjects can choose to withdraw consent for use of their data during the study, and they will be fully removed. Subjects can also choose to withdraw from the intervention, but continue in the study where their data will be collected and analyzed.

7. Data and Specimens

Data and protected health information will be safeguarded in multiple ways. First, all study forms will include only a study ID number. Actigraphy devices will be configured with only an ID number and will not store any identifiers. The key to study ID and patient identifiers will be maintained by the PI in a secure REDCap database that is password protected and hosted on the OHSU secure server. All study data will be inputted into REDCap by members of the study team. The PI will maintain the REDCap database and provide access only to study team members. All exports of data from REDCap will be coded.

All potential physical discomforts related to actigraphy devices will be minimized by allowing participants to remove the device if discomfort occurs and to withdraw from this portion of the study if desired. The actigraphy data will be collected using Fitbit devices.

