The Fitbit mobile app and device require the creation of individual accounts with Fitbit for all study participants within the Fitbit app on a smart phone or tablet. Participants will be asked to use an email address of their choosing and accept Terms and Conditions for use of the Fitbit app. The data collected from the Fitbit devices will NOT be integrated with the medical record of the patient or used for clinical decision making. FitBit data will be collected through syncing with the FitBit app on a smart phone or tablet at least weekly by the participant. The Fitabase platform will be used to remotely collect real-time physical activity and sleep data from study participants' Fitbit accounts, and also to send personalized text messages to participants' cell phones. Participants will be asked to accept the Fitabase Terms and Conditions for linking with the Fitbit App. Fitabase is a secure password-protected web-based platform hosted in a HIPAA-compliant server. Fitabase comprises user-friendly visualization and data exportation tools that allow key research personnel to view participants' Fitbit data in the form of graphs every time participants sync their wearable tracker with the Fitbit mobile app. Study participants will not have access to Fitabase; they will only interact with the Fitbit mobile app and activity tracker. The text messaging feature is integrated with Fitabase and utilizes Twilio's application programming interface to send messages via the SMS protocol. Participants will be consented to utilize their smart phone devices for syncing with the Fitbit app and to receive text messages from the platform to serve as reminders to sync devices and to utilize the online resources for those in the intervention phase. The only identifier shared with the Fitabase platform and Twilio, Inc. is the telephone number for the smart phone device the participant consents to utilize. Participants will be asked to use and email address of their choosing to create an account within the Fitbit App.

All risks associated with the intervention will be minimized by allowing participants to discontinue the intervention at their discretion and the study team will regularly assess adverse effects of the intervention.

If participants suffer any unforeseen harms including psychological, emotional, physical, they will be encouraged to contact the PI or the IRB. Contact information will be provided in the consent forms including telephone, mail, and email.

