As this trial is a pilot investigation, we do not have prespecified stoppage criteria. Trial progress and safety will be closely monitored by the PI and DSMB. The PI will review Serious Adverse Events (SAEs) as they occur and the DSMB will review SAEs at each meeting and on an as-needed basis. The DSMB will review trial progress and safety. The DSMB recommendations may include study continuation without modification, study termination, study continuation with protocol modification, or temporary suspension of enrollment until further evaluation is completed. The DSMB will review each death occurrence. Cumulative SAEs for each study arm will be provided to the DSMB and reports will be submitted to the study team, IRB, program staff at the National Institutes of Health, and the Food and Drug Administration as required. If the PI is notified of any SAE that is thought possibly related to the study, the participant will be immediately withdrawn.

11. Risks and Benefits

a. Risks to Subjects

Intervention risks will be considered more than minimal risk, but with potential to directly benefit the participant. Melatonin has demonstrated a good safety profile in multiple studies involving children and is available as a dietary supplement over the counter. A concern regarding use of over the counter melatonin is the variability in content and contaminants within supplements noted from lack of FDA oversight of dietary supplements.[87] We have minimized this risk by working with a manufacture that has provided Chemistry and Manufacturing Control data reviewed and approved for use by the FDA IND application. No serious adverse events have been reported with melatonin use in short or long-term studies as noted above. Studies using melatonin have reported symptoms including: dermatologic (itchy skin, rash), gastrointestinal (stomach upset, appetite changes, emesis), neurologic (drowsiness, blurred vision, vivid dreams), and bodily pain. Placebo studies report similar symptoms. Melatonin may affect levels of medications metabolized in the liver (particularly through CYP1A2 and CYP450 enzymes) or that are conjugated in the liver to sulfuric or glucuronic acid. There are unclear effects of melatonin on auto-

immune disorders and immune function. Melatonin is considered a dietary supplement, and as such, not regulated by the Food and Drug Administration. All risks will be communicated to the participant and included in the written consent provided to participants.

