No serious adverse events were reported in recent meta-analyses of studies using melatonin conducted in children with neurodevelopmental disorders, including epilepsy, or in a recent adult trial comparing melatonin and placebo, but melatonin appeared to effectively improve sleep. No serious adverse events were reported in a recent randomized trial in pediatric concussion using doses up to 10mg (double this trial's maximum dosing).[76] The potential benefit of improved sleep after TBI in our study compared to the risk associated with melatonin is likely as favorable to standard care given >50% have disturbed sleep after discharge without treatment and SWD are associated with worse cognitive functions and quality of life in pediatric TBI patients.

Given the ubiquitous use of melatonin in pediatric clinical care and research studies in a variety of pediatric populations with medical, developmental, and psychiatric disorders, no patients will be excluded for underlying medical conditions or concomitant medication use, outside of exclusion criteria above. Patients will be excluded from the trial if the clinical care Attending Physician deems the patient unable to tolerate enteral medications or otherwise has safety concerns regarding use of melatonin.

There will be no requirement for use of contraception in female participants of child-bearing age given no known adverse effects of melatonin in pregnancy and short duration of the intervention. Pregnant patients will be excluded from the trial or withdrawn immediately from the trial if become pregnant.

The educational intervention proposed in this study is of minimal risk given it is a handout with resources to promote healthy sleep. As part of our acceptability outcomes, we will evaluate utilization and usefulness of this portion of the intervention.

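### Pregnancy takes a participant out of the trial, and a possibly related SAE leads to withdrawal from an unstated object; the plan should say that 30-day follow-up continues after either stop

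*Combined protocol and SAP*

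**What the plan says.** Two rules let the study team end participation. For a serious adverse event, Section 10 says: "If the PI is notified of any SAE that is thought possibly related to the study, the participant will be immediately withdrawn". For pregnancy, Section 11a says the participant is "withdrawn immediately from the trial if become pregnant".

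Two other statements concern stopping the intervention, and both leave it to the participant. The end of Section 6 says: "Subjects can also choose to withdraw from the intervention, but continue in the study where their data will be collected and analyzed". Section 7 describes risk control by "allowing participants to discontinue the intervention at their discretion".

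The outcomes that depend on follow-up are in Section 6, Table 1. Retention is a primary feasibility outcome, measured as "Number completed/consented; Goal >90" percent; the table does not define completion. Adverse events are a primary acceptability outcome, taken from a participant symptom checklist and from medical record review. The Sleep Disturbances Scale for Children (SDSC) total score at 30 days is also starred as primary, but sits under the exploratory effectiveness heading. On timing, Section 6 says: "30-day outcomes assessments will be defined from the time of study intervention initiation". Section 8 plans both intention-to-treat and per-protocol analyses.

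**The concern.** Intention-to-treat analysis needs outcomes from participants who stop treatment as well as from those who stay on it. Section 6 recognises this by separating leaving the intervention from leaving the study, but it gives the option only to participants who choose it. Nothing supplied extends it to a participant stopped by the study team for an SAE or pregnancy.

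If such a participant leaves the study, the 30-day SDSC, the other questionnaires, the symptom checklist and the satisfaction survey are not collected. For a possibly related SAE this missingness is tied to how the child fared on the assigned product, and the family's later report is then most informative about acceptability. A family willing to finish could also be counted against retention. The drop-out question, "Please tell us your reasons for leaving the trial", does not fit a departure that the study team decided.

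**Working it through.** The plan states no figure on this point, so there is none to reproduce. The check is a comparison of the texts, followed by arithmetic on scale.

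**Texts side by side**

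| Trigger | Who decides | Withdrawn from | Follow-up stated? |
|---|---|---|---|
| Participant stops the intervention (Sections 6, 7) | Participant | Intervention | Yes, in Section 6 |
| Possibly related SAE (Section 10) | Study team | Not stated | No |
| Pregnancy (Section 11a) | Study team | Trial | No |

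The pregnancy row is explicit. The SAE row can be read either way.

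**What is lost and what is kept on the study-withdrawal reading**

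- Lost: the 30-day questionnaires, symptom checklist and satisfaction survey.
- Kept: the triggering SAE, and events found by medical record review (Table 1; Section 10). Data already collected are also kept, because Section 6 removes data only when a participant withdraws consent for their use.

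**Retention**

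Inputs: 30 to 50 participants (Section 5a), taken as the number consented, and a goal above 90% (Table 1). The cost of one case is 100/n points. The allowance is the largest k for which (n − k)/n exceeds 0.90.

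| n | Cost of one case | Largest loss that meets the goal | One more loss |
|---|---|---|---|
| 30 | 3.3 points | 2 (28/30 = 93.3%) | 27/30 = 90.0%, misses |
| 40 | 2.5 points | 3 (37/40 = 92.5%) | 36/40 = 90.0%, misses |
| 50 | 2.0 points | 4 (46/50 = 92.0%) | 45/50 = 90.0%, misses |

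One case therefore uses half of the allowance at 30 and a quarter at 50, provided it is counted as a non-completer.

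**Number of cases (assumed rates)**

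The documents give no rate for these withdrawals. At assumed rates p of 0.5%, 1% and 2% for both reasons together, the expected number n × p is 0.15, 0.30 and 0.60 at n = 30, and 0.25, 0.50 and 1.00 at n = 50. The chance that these withdrawals alone miss the goal is binomial: P(X ≥ 3) at n = 30 is 0.05%, 0.3% and 2.2%; P(X ≥ 5) at n = 50 is at most 0.3%.

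Adding ordinary drop-out at an assumed rate q makes the total loss rate 1 − (1 − q)(1 − p). At n = 50 and p = 1%, the chance of missing the goal rises from 0.3% to 1.6% for q = 2%, from 10% to 18% for q = 5%, and from 57% to 65% for q = 10%. The choice of q largely sets the answer, so none of these is an estimate for this trial.

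**SDSC (assumed effect)**

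Suppose one participant missing from an arm of m would have scored d standard deviations worse than the rest of that arm. The arm mean then shifts by d/m. For d = 0.5 to 1, this is 0.033 to 0.067 SD at m = 15 and 0.020 to 0.040 SD at m = 25. The standard error of the arm difference is √(2/m) SD, which is 0.37 at 15 per arm and 0.28 at 25. The shift is thus 7% to 18% of one standard error.

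**The case against.** The SAE rule names no object, and Section 6 already distinguishes the intervention from the study, so withdrawal from product is an available reading. Section 10 also refers to a separate DSMP that may define it. This stands: the SAE half is an ambiguity, not a demonstrated loss. It does not help with pregnancy, where the text names the trial.

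A reader might infer that safety information disappears. The documents do not support that. A participant with a possibly related SAE already counts as having had an adverse event, record review continues to supply events, and Section 10 sends cumulative SAEs by arm to the monitoring board.

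A reader might also infer that missingness is ignored. Section 8 plans to examine missing 1-month outcomes and to compare completers with drop-outs. That stands as a safeguard, although it describes the loss and does not recover the data.

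Finally, telling staff to stop the product and nothing else would be wrong. The SAE rule covers events related to the study, which could include the wearable device. Pregnant patients are also excluded under Section 5, including its Vulnerable Populations part, and Section 11a cites no known harm of melatonin in pregnancy. The pregnancy rule may therefore concern who may take part in this research, not only exposure. Both points stand and shape the fix.

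**Conclusion.** The point holds as a minor, inexpensive improvement. The pregnancy rule as written, and the SAE rule if it means leaving the study, give up participant-reported 30-day data after a post-randomisation event, and the planned intention-to-treat analysis would want those data. The clearer text concerns pregnancy, where missingness is less likely to depend on the assigned arm. The case that matters more for bias, a possibly related SAE, is the one left ambiguous.

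The size is 2.0 to 3.3 points of retention per case, on the assumptions that 30 to 50 participants consent and that such a case counts as a non-completer. Few cases are expected, but this is a judgement: the documents supply no rate, and Section 11a reports no serious adverse events in the melatonin studies it cites.

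A reader might go further and conclude that the retention goal is in danger or that the effectiveness comparison is materially biased. The documents do not support either. The first needs assumed event and drop-out rates, and a missed benchmark has a mild consequence: "If feasibility benchmarks are not met, study procedures and the protocol will be reviewed". For the second, the SDSC comparison is exploratory, and one case shifts it by a small fraction of its standard error.

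**What to change.** In Section 10, state that a possibly related SAE stops the study product and any other study procedure suspected of causing it. In Section 11a, state that pregnancy stops the study product. In both, add that, unless consent is withdrawn and, for pregnancy, if the IRB agrees:

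- adverse-event follow-up and the 30-day questionnaires continue by phone, electronic survey or chart review;
- the participant is analysed in the randomised arm under intention to treat;
- if the 30-day assessment is done, the case is reported as *discontinued intervention, completed follow-up*, separately from drop-outs, with the study team's reason recorded.

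Align the SAE wording with the DSMP. The clinical rule on when the product stops does not change.

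The cost is a short addition to each section and one reporting category. No new visit is needed, because the 30-day assessment runs from the start of the intervention and Section 6 already allows remote collection. There are two downsides. Some 30-day data will reflect time off product, so these cases need a flag in the pill-count adherence figure; the planned per-protocol analysis can be shown alongside. The pregnancy wording also needs IRB confirmation. If enrolment has finished, such cases can still be reported separately and the wording carried into the larger trial.

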	
adherent if device worn for ≥5 nights consecutively; we will assess sleep routines through actigraphy; will be counted as unknown if did not participate in the actigraphy portion
 
Quantitative survey: "How many nights each week did you take the study medication since discharge?"
 
None, 1-3, 3-4, 5-7, All
 
Quantitative survey response: "Did you receive sleep education with your hospital discharge paperwork?"; choices of a) did not receive discharge paperwork; b) I did not receive any sleep education at discharge; c) I received it, but did not use it; d) I received it, but did not find it helpful; e) I received it, and found it helpful; responses to this question will also be compared with the discharge instructions within the electronic health record to determine if the resource was provided as intended.
	Descriptive percent; Chi-square to compare intervention arms
Acceptability Outcomes		
*Adverse Events (discharge, 30-day)	
Qualitative response to survey: "Did you have any new medical problems since the last study visit?"
 
Quantitative yes/no response: "Did you have any of the following symptoms since the last visit"
 
 a. Nausea b. Vomiting c. Diarrhea d. Drowsiness e. Fatigue f. Headache g. Behavioral changes h. Vivid dreams i. Nightmares j. Waking up at night k. Itchy skin l. Rash m. Appetite changes n. Bodily pain or aches o. Chest pain p. Enuresis or bedwetting q. Dizziness r. Tinnitus or ringing in the ears s. Feeling cold 
Evaluation of medical record, patient assessments to quantify adverse events and unexpected problems collected as a dichotomized yes/no and number of events
	
Thematic analysis
 
Descriptive percent and mean with standard deviation; Chi-square (yes/no) and Mann-Whitney U test (continuous) to compare intervention arms

Satisfaction (30-day)	Quantitative rankings on a likert scale survey: experiences with the study overall, consent process, study team, study intervention, questionnaires, Actigraphy devices, care received	Descriptive median and interquartile range; Mann-Whitney U tests

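### Blurred vision is the only symptom in the risk section with no item on the Table 1 symptom checklist, so it is not systematically solicited and is probably under-recorded

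*Combined protocol and SAP*

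**What the plan says.** Section 11a (Risks to Subjects) groups the symptoms reported in melatonin studies as "dermatologic (itchy skin, rash), gastrointestinal (stomach upset, appetite changes, emesis"), then "neurologic (drowsiness, blurred vision, vivid dreams"), and lastly bodily pain. The next sentence qualifies the list: "Placebo studies report similar symptoms".

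In Section 6, the Adverse Events row of Table 1 is marked as a primary outcome and collected at discharge and at 30 days. It has three parts:

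- an open question about new medical problems, assigned to thematic analysis;
- a closed yes/no list introduced by "Did you have any of the following symptoms since the last visit";
- an evaluation of the medical record and patient assessments to quantify events.

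The closed list begins "a. Nausea b. Vomiting c. Diarrhea d. Drowsiness e. Fatigue f. Headache g. Behavioral changes h. Vivid dreams i. Nightmares", continues "j. Waking up at night k. Itchy skin l. Rash m. Appetite changes n. Bodily pain or aches o. Chest pain", and ends with bedwetting, dizziness, tinnitus and feeling cold (items p to s). That makes 19 items.

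Section 10 adds a clinic visit to survey and record review as a source at 30 days, and says that every adverse event is to be recorded. Section 8 analyses adverse events as yes/no and as a total per patient, compared between arms by chi-square and Mann-Whitney tests.

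**The concern.** The checklist is wider than the risk section. Twelve of its 19 items, such as tinnitus, chest pain and feeling cold, are not among the nine symptoms listed in Section 11a. Yet it leaves out one symptom that Section 11a does name, and no reason is given. Section 11a also says that the risks will be put in the written consent, so families are to be told of blurred vision but not asked about it by name.

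A prompted symptom is normally reported more often than one that must be volunteered. A family may not think of a mild or passing visual symptom as a new medical problem, and a chart holds only what a clinician wrote down. The pilot is meant to inform a larger trial, so a low count for this symptom could reflect how it was collected rather than how often it occurred.

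**Working it through.** **Step 1: match the two lists.** The plan has no figure of its own to reproduce here; the check is item by item.

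| Section 11a symptom | Checklist item in Table 1 |
|---|---|
| Itchy skin | k |
| Rash | l |
| Stomach upset | approximate: a, b, c (nausea, vomiting, diarrhea) |
| Appetite changes | m |
| Emesis | b (vomiting) |
| Drowsiness | d |
| Blurred vision | none |
| Vivid dreams | h |
| Bodily pain | n |

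Seven of nine match directly, one approximately and one not at all. Dizziness (q) is not a visual symptom and does not stand in for blurred vision.

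**Step 2: what the missing prompt could do to the recorded rate.** Inputs:

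- Arm size n = 15 or 25, from the 30 to 50 patients in Section 5a randomized 1:1.
- True incidence p in the melatonin arm: not in the documents; assumed 10% or 2%.
- Chance v that a case is recorded without a prompt: not in the documents; assumed 30%.
- A direct question is taken to catch every case, and every patient is taken to be followed up.

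Probability that the arm records no case:

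- asked directly: (1 − p)^n
- not prompted: (1 − v·p)^n

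| p | n per arm | Asked directly | Not prompted, v = 30% | Gap (points) |
|---|---|---|---|---|
| 10% | 15 | 0.90^15 = 20.6% | 0.97^15 = 63.3% | 42.7 |
| 10% | 25 | 0.90^25 = 7.2% | 0.97^25 = 46.7% | 39.5 |
| 2% | 15 | 0.98^15 = 73.9% | 0.994^15 = 91.4% | 17.5 |
| 2% | 25 | 0.98^25 = 60.3% | 0.994^25 = 86.0% | 25.7 |

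The result depends on v. At v = 100% the gap is zero, because the other sources catch everything. At v = 0 no case is ever recorded.

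**Step 3: what it does to the planned comparisons.** Suppose the checklist answers feed the Section 8 measures. A missing item changes a patient's yes/no result only if unrecorded blurred vision was that patient's sole event. It lowers a patient's total by at most one per assessment, so by at most two over discharge and 30 days. The checklist is the same in both arms, and Section 6 blinds participants and outcome assessors, so v should be the same in both. The recorded difference in this symptom is then v × (p_melatonin − p_placebo): a true difference is shrunk, and none is created.

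**The case against.** A reader might infer that the trial never asks about blurred vision at all. The documents do not support that. The open question could bring it out, Table 1 adds the medical record and patient assessments, and Section 10 adds the clinic visit. What can be said is that none of these prompts for the symptom by name, as the checklist does for the others.

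A reader might also call blurred vision an expected harm of melatonin. Section 11a goes no further than saying it has been reported, gives no rate, and notes similar symptoms on placebo. That weakens any claim of a melatonin-specific risk. It does not remove the reason to ask, since the same prompt in both arms is what would show whether the rates are alike.

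Three further objections have force:

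- Nothing requires the checklist to mirror the risk section, so this is a gap in ascertainment and not a contradiction.
- The separate Data and Safety Monitoring Plan mentioned in Section 10 may hold more detail and is not available here.
- The 30% volunteering rate is a guess. Families told of the symptom at consent, together with chart review and a clinic visit, could push it higher.

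The same argument might be extended to stomach upset. It does not carry over: nausea, vomiting, diarrhea, appetite changes and bodily pain are already listed. Another overlapping item could count one complaint more than once in the total if items are summed.

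**Conclusion.** The point holds as a minor one. Blurred vision is the one symptom named in Section 11a without a checklist counterpart, and its descriptive rate is likely to be under-ascertained relative to the prompted symptoms. The item match is a fact of the documents. The size is illustrative: over the assumed incidences of 2% and 10% and the two arm sizes, with 30% volunteered, leaving out the prompt raises the chance of recording no case in the melatonin arm by roughly 17 to 43 percentage points. At 2% incidence a trial of this size would usually see no case even if it asked.

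The documents do not support reading this as a threat to the primary adverse event comparison. Section 8 plans no test per symptom, the effect on the yes/no and total measures is small, and it is not differential by arm.

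**What to change.** Add blurred vision as one more yes/no item on the Table 1 checklist, asked at discharge and at 30 days in both arms, or state why it is left to unprompted reporting. Make the matching change in the REDCap survey. No separate stomach-upset item is needed. The cost is one more survey item at each assessment, with no effect on design, sample size or analysis method. If patients have already answered the present checklist, report this symptom only for those who were asked, with that denominator.
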